4.1 Phase II Study Assessment Tables

 Initial Study Assessments Table 												
*Evaluations are completed weekly, every 7 days ± 3 days												
Nu-V3 Treatment Arm Evaluation*	Week 1	Week 2	Week 3	Week 4	Week 5	Week 6	Week 7	Week 8	Week 9	Week 10	Week 11	Week 12
Informed Consent	x											
Inclusion and Exclusion ¹	x											
Patient Registration ¹	x											
Medications Form ¹	x			x				x				x
Patient Onboarding and Orientation ²	x											
In office assessment	x	x	x	x	x	x	x	x	x	x	x	x
New Device Placed ³	x				x				x			
Pad Replaced ³		x	x	x		x	x	x		x	x	x
Treatment Forms ¹	x	x	x	x	x	x	x	x	x	x	x	x
No Device												
HRV Assessment (optional) ⁴	x	x	x	x	x	x	x	x	x	x	x	x
ePRO Questionnaires ⁵	x	x	x	x	x	x	x	x	x	x	x	x
Patients' Global Impression of Change ePRO form (PGIC) ⁵		x	x	x	x	x	x	x	x	x	x	x
Providers' Global Impression of Change ePRO form (PGIC) ¹		x		x		x		x		x		x
Optional Patient Media Testimony ⁶	x	x		x				x				x

1. Inclusion/Exclusion, Registration, Medications, Treatment, and Providers' PGIC forms to be completed by site via online module.
2. Patient Onboarding and Orientation includes introductory demographics form, Nu-V3 patient training video
3. Upon having three consecutive weeks of primary symptom reduction of $\geq 70\%$ via patient reported numerical scales from baseline, the participant will have reached symptom response plateau and will continue as described in the study assessments table, but without device therapy. Then if the participant's primary symptom score increases at any time by $\geq 20\%$ from the symptom response plateau, they may again continue device therapy until week 24.
4. (Optional) HRV assessment will be conducted before the first treatment and again 15-20 minutes following the first treatment. The HRV assessment will also be conducted prior to each weekly treatment. This assessment is applicable to participating sites per the clinical trial agreement. Contact the clinical trial manager for Information.
5. ePRO questionnaires completed on patient's mobile device: DQ-9 (baseline), PTB-7, PEG, GAD-7, PHQ-9, PROMIS 4a, PGIC
6. If patient consents to media testimony, site will collect via study collection process.

Nu-Life Solutions Miniaturized Wearable Medical Technology - NuJ ³	Study Assessments Table											NuJ ³
	*Evaluations are completed weekly, every 7 days ±3 days											
Nu-V3 Treatment Arm Evaluation*	Week 13	Week 14	Week 15	Week 16	Week 17	Week 18	Week 19	Week 20	Week 21	Week 22	Week 23	Week 24
Medications Form ¹				x				x				x
In office assessment	x	x		x	x		x	x		x	x	x
New Device Placed ²	x			x			x			x		
Pad Replaced ²		x			x			x			x	
Treatment Forms ¹	x	x		x	x		x	x		x	x	
No Device			x			x			x			x
HRV Assessment (optional) ³	x	x		x	x		x	x		x	x	
ePRO Questionnaires ⁴	x	x	x	x	x	x	x	x	x	x	x	x
Patients' Global Impression of Change ePRO form (PGIC) ⁴	x	x	x	x	x	x	x	x	x	x	x	x
Providers' Global Impression of Change ePRO form (PGIC) ¹		x			x			x		x	x	
Optional Patient Media Testimony ⁵	x	x		x				x				x

1. Providers' PGIC form, Medications and Treatment forms to be completed by site via online module.
2. Upon having three consecutive weeks of mean symptom reduction of ≥70% via patient reported numerical scales, the participant will continue as described in the study assessments table, but without device therapy. Then if the participant's primary symptom score increases at any time by ≥20%, they may again continue device therapy until week 24.
3. (Optional) HRV assessment before the first treatment and again 15-20 minutes following the first treatment. HRV assessment will also be conducted prior to each weekly treatment. This assessment is applicable to participating sites per the clinical trial agreement. Contact the clinical trial manager for information.
4. ePRO questionnaires completed on patient's mobile device: DQ-9 (baseline), PTB-7, PEG, GAD-7, PHQ-9, PROMIS 4a, PGIC
5. If patient consents to media testimony, site will collect via study collection process.

Nu-Life Solutions Miniaturized Wearable Medical Technology - NuJ ³	Control Study Assessments Table											NuJ ³
	*Evaluations are completed weekly, every 7 days ±3 days											
Control Arm Evaluation*	Week 1	Week 2	Week 3	Week 4	Week 5	Week 6	Week 7	Week 8	Week 9	Week 10	Week 11	Week 12
Informed Consent	x											
Inclusion and Exclusion ¹	x											
Patient Registration ¹	x											
Medications Form ¹	x			x				x				x
Patient Onboarding and Orientation ²	x											
In office assessment	x			x				x				x
No Device	x	x	x	x	x	x	x	x	x	x	x	x
ePRO Questionnaires ³	x			x				x				x
Patients' Global Impression of Change ePRO form (PGIC) ³				x				x				x

1. Inclusion/Exclusion, Registration, Medications, Treatment, and Providers' PGIC forms to be completed by site via online module.
2. Patient Onboarding and Orientation includes introductory demographics form, Nu-V3 patient training video
3. ePRO questionnaires completed on patient's mobile device: DQ-9 (baseline), PTB-7, PEG, GAD-7, PHQ-9, PROMIS 4a, PGIC

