4.0 STUDY PROTOCOL

The Nu-V3 Clinical Study is a randomized, open-label study using the Nu-V3 cranial nerve stimulation treatment device in patients with chronic pain, anxiety, depression, and/or sleeplessness. Study participants are those who have signed the informed consent form, met the inclusion and exclusion criteria, and are enrolled in the study at one of multiple sites.

Subjects randomized to receive the Nu-V3 treatment will undergo the following regimen:

- At the baseline visit, patients will be asked to complete study questionnaires (Appendix 11) regarding all of the following symptoms: chronic pain, anxiety, depression, and/or sleeplessness, as well as their quality of life, active medications, medical history, and demographical information. The subject's primary symptom of concern will also be notated at baseline, for later assessment of continuation after week 12.
- At each subsequent visit, patients will be asked to complete study questionnaires regarding all the following symptoms: chronic pain, anxiety, depression, and/or sleeplessness, as well as their activity level and quality of life.
- The sessions will begin with the Nu-V3 device being clipped on the ear and three small pads (non-invasive) adhered to the surface of the ear. Each Nu-V3 device lasts for up to 28 days with a change in the pads approximately 7 days into the treatment.
- Each session takes approximately 15-20 minutes. The placement of the device takes approximately 5 minutes, and the remaining time is spent verifying ePRO form completion, and evaluating the patient for all device effects.
- The Nu-V3 device is mobile and is worn externally on the left ear 24 hours a day during treatment, fitting comfortably behind the ear. An electrical signal is sent to

the external ear through coated wire leads attached to the device and adhesive pads which attach to three sites on the ear.

- Participants should be able to perform their typical day-to-day activities while wearing the device. They may shower while wearing the Nu-V3 device, if they do not get the device wet and use the small disposable ear covers that are provided for them.
- In the event the Nu-V3 gel pads are inadvertently removed or the device comes off, the participant will contact the site coordinator. The participant is encouraged to adjust the device placement as needed for comfort.
- Patients should not change their existing forms of treatment or medications without discussion with the study investigator.

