Subjects randomized to the observation control arm of the study will undergo the following regimen:

- At the baseline visit, patients will be asked to complete study questionnaires (Appendix 11) regarding all the following symptoms: chronic pain, anxiety, depression, and/or sleeplessness, as well as their quality of life, active medications, medical history, and demographical information. The subject's primary symptom of concern will also be notated at baseline.
- At each subsequent visit, patients will be asked to complete study questionnaires regarding all the following symptoms: chronic pain, anxiety, depression, and/or sleeplessness, as well as their activity level and quality of life.
- Patients should not change their existing forms of treatment or medications without discussion with the study investigator.
- At completion of 12 weeks of standard of care treatment post study enrollment, observation (control arm) subjects will be offered a crossover into the treatment arm of the study for an additional 24 weeks.

Sample size

For this Phase II study, a total of 100-200 subjects will be randomized 1:1 to either the Nu-V3 treatment arm or to the observation treatment arm (SOC, control).

Recruitment

Participants are enrolled into relevant symptom cohorts based on their chronic pain, anxiety, depression, and/or sleeplessness symptom presentation at baseline and treated with the Nu-V3 device for 24 weeks.

Analyses

Interim analysis of reported data will be based on baseline symptom cohort and conducted at 6, 12, 18, and 24 weeks during this time. The participant will be evaluated after the initial 12-week treatment period to assess for further therapeutic need. Upon having three consecutive weeks of mean symptom reduction of $\geq 70\%$ via patient reported numerical scales, the participant will continue as described in the study assessments table, but without device therapy. Then if the participant's primary

symptom score increases at any time by $\geq 20\%$, they may again continue device therapy until week 24, as depicted in section 4.1.

Study subjects randomized to the observation arm will be offered the opportunity to cross-over to the Nu-V3 study treatment arm upon completion of the initial 12-week observation study period.

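### The rule for taking a responder off the device is stated two ways: 70% reduction in the primary symptom in one place, 70% in an undefined mean in two others

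*Protocol*

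**What the plan says.** The stop rule appears three times.

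- **Section 4.1, weeks 1–12 treatment-arm table, footnote 3:** "Upon having three consecutive weeks of primary symptom reduction of" at least 70% from baseline, after which the participant is said to have reached a plateau and continues without the device.
- **Section 4.0, Analyses:** "Upon having three consecutive weeks of mean symptom reduction of" at least 70%, with neither the mean nor the reference value stated.
- **Section 4.1, weeks 13–24 table, footnote 2:** "Upon having three consecutive weeks of mean symptom reduction of ≥70% via patient reported numerical scales", again with neither stated.

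The restart rule follows each time and always concerns the primary symptom score. Footnote 3 measures the 20% rise "from the symptom response plateau, they may again continue device therapy until week 24". Footnote 2 says only "primary symptom score increases at any time by ≥20%, they may again continue device therapy until week 24". Section 4.0 gives no reference itself but ends "they may again continue device therapy until week 24, as depicted in section 4.1".

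On timing, the treatment-arm regimen in Section 4.0 has the primary symptom "notated at baseline, for later assessment of continuation after week 12". The Analyses paragraph says: "The participant will be evaluated after the initial 12-week treatment period to assess for further therapeutic need". Footnote 3, however, is attached to the device and pad rows for weeks 1–12. No text gives a first week for the rule.

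**The concern.** Sites apply this rule at visits to decide whether a participant wears the device, so it is not a detail that can wait for an analysis plan. Two sites following different sentences could treat the same responder differently, and the regimen evaluated in the Nu-V3 arm would depend on which sentence was read. The choice also affects follow-up: Section 7.0 asks for in-person toxicity assessment at treatment visits and accepts telephone contact once a stabilized participant is off the device.

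Two smaller points need clearing up at the same time. The placement of footnote 3 suggests that the rule could act before week 12, while Section 4.0 puts the continuation decision after it. Footnote 2 also leaves out the restart reference that footnote 3 gives.

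**Working it through.** The protocol gives no figure to reproduce. The check is whether the two wordings can lead to different decisions, and over how many weeks. All symptom scores below are assumed for illustration.

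**1. Mean over the four symptoms.** Section 8.1 lists four instruments. Let *p* be the percentage reduction in the primary symptom and *x* the average reduction in the other three. The mean rule requires (p + 3x)/4 ≥ 70, that is x ≥ (280 − p)/3.

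- p = 80: x ≥ 200/3 = 66.7%.
- p = 100: x ≥ 180/3 = 60%.

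Below these values footnote 3 stops the device and the mean wording keeps it on.

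**2. Mean of the primary symptom over the three weeks.** Reductions of 60, 72 and 81% average (60 + 72 + 81)/3 = 71%, so the device stops. Under footnote 3, read naturally as requiring 70% in each week, the 60% week fails and the device stays on. The disagreement now runs the other way.

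**3. Mean over the items of the primary instrument.** The PEG score is already the average of its three items (Section 8.1), so for pain the two wordings agree.

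Two of the three readings therefore conflict with footnote 3, and the protocol does not choose among them.

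**4. Exposure affected after week 12.** The weeks 13–24 table schedules a device or pad in weeks 13, 14, 16, 17, 19, 20, 22 and 23, which is 8 weeks; weeks 15, 18, 21 and 24 are marked as without device. All 8 differ only if one version is met by week 12, the other is never met and there is no restart. Eight is an upper bound, not an expected value.

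**5. Whether weeks before 13 count.** If weeks 10, 11 and 12 can qualify, the first stop is at week 13 and 0 of the 8 later device weeks are worn. If only weeks 13, 14 and 15 can qualify, the first device withheld is at week 16 and 2 of the 8 are worn.

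**6. Can 70% be reached on every scale?** The protocol gives no scoring for PROMIS 4a. Assume the four items printed in Appendix 8 score 1 to 5, for a raw range of 4 to 20. A 70% reduction from baseline *b* needs 0.3b ≥ 4, so b ≥ 13.3, and a participant with a raw baseline below 14 could never meet the rule. If items score 0 to 4, or the minimum is subtracted, the difficulty disappears.

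**The case against.** The best defence is to read the protocol as a whole. The primary symptom is recorded for the continuation decision, footnote 3 stops on it, and every restart sentence uses it, so the primary symptom governs and a four-symptom mean is the least supported reading. This has force. It still leaves open whether three weeks are averaged or each must qualify, and step 2 shows that this alone can reverse the decision.

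It may also be said that the two tables intend different rules for two phases. The protocol never says so. Section 4.0 states the mean version generally and points to Section 4.1, which holds both, and footnote 3 permits restart up to week 24, inside the period of the second table.

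Three stronger readings are tempting, and the documents do not support them.

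- **That exposure before the week-12 comparison is compromised.** This needs footnote 3 to act as placed. Section 4.0 puts the continuation assessment after week 12, and the weeks 1–12 table schedules a device or pad every week and leaves its no-device row empty. The placement leaves some real doubt but no more.
- **That the restart threshold is contradictory.** Footnote 2 is silent, not in conflict. Section 4.0 refers to Section 4.1, where the plateau is the only reference given. No text suggests 20% of baseline, and restart is permitted, not required.
- **That the reference for the 70% reduction is in dispute.** Footnote 3 names baseline, Section 8.1 measures reduction from baseline, and no other reference is suggested.

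**Conclusion.** The contradiction between primary-symptom reduction and an undefined mean reduction is real and should be corrected. It can change whether the same responder stops or continues the device, mainly in weeks 13–23, with at most 8 scheduled device weeks at issue under the conditions in step 4. It therefore bears chiefly on the 24-week time point, which falls after controls may cross over.

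A reader might infer that the trial's comparison is biased or invalid. That does not follow: analysis by randomized arm remains valid, and what is unclear is the regimen being evaluated. The protocol gives no basis for estimating the effect on outcome. Confidence is high for the wording conflict. The placement of footnote 3 and the restart reference missing from footnote 2 are secondary clarifications.

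**What to change.** Use one sentence, identical in Section 4.0 (Analyses) and in both Section 4.1 tables: the device stops when the primary symptom is at least 70% below baseline at each of three consecutive weekly assessments, and restart is permitted when it rises by at least 20% from the plateau. Say which score is the plateau, for example the third qualifying one.

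State that the rule first acts at the week-13 visit, with weeks 10, 11 and 12 as the earliest qualifying run, and remove footnote 3 from the weeks 1–12 device and pad rows.

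Name the weekly scale used for each primary symptom. Section 3.1 uses the term primary symptom score for the Baseline Symptom Questionnaire, which is not among the weekly questionnaires listed in Section 4.1. Score each scale so that a 70% reduction is attainable; for PROMIS 4a, subtract the minimum raw score so that the scale starts at zero.

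The cost is protocol wording and site retraining, with no new data collection. Compared with footnote 3 applied as placed, early responders would wear the device longer. In the extreme case of qualifying at weeks 2, 3 and 4 with no restart, that is 13 − 4 = 9 weeks up to the week-13 visit, on a device that Section 1.3 classes as nonsignificant risk.

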5.0 DATA COLLECTION AND RETENTION

The study endpoints data will be collected from each participant's study questionnaires. The data will be collected electronically via the patient's own device and uploaded to an electronic data capture system. The data will be used to measure whether the Nu-V3 device provides participants with a reduction in participants' chronic pain, anxiety, depression, and/or sleeplessness.

The data analysis will include baseline data for each participant's questionnaire prior to beginning treatment with the Nu-V3 device. Longitudinal data will consist of participant's weekly questionnaires measuring chronic pain, anxiety, depression, and sleeplessness during the treatment phase. The final data collection will be completed by participants at the end of the treatment with the Nu-V3 device and will measure chronic pain, anxiety, depression, and sleeplessness.

The Principal Investigator at each site will be responsible for recording, collecting, and storing the research participant's study data. The written records will be stored in a secure location. Only the Principal Investigator or designated study staff will have access to the study records and all electronic files will be password protected. The Principal Investigator will also maintain adequate records for the study including:

- all correspondence with the IRB and Sponsor
- other pertinent data related to the study

All records are to be retained by the Principal Investigator for a period of three (3) years following the closure of the study. Following study closure, the Principal Investigator shall inform Nu-Life of the location of study records and storage changes (i.e., the Principal Investigator leaves the institution where the study was conducted). In such cases, the study records may be transferred to another institution, investigator, or to Nu-Life upon written agreement between the Principal Investigator and Nu-Life.

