8.0 STUDY ENDPOINT and DATA ANALYSIS

8.1 Primary Endpoints: Primary endpoints consisted of the following:

Safety: At screening/baseline, a medical history will be obtained to capture relevant underlying conditions. The screening/baseline examinations will include BP, and HR. Baseline signs and symptoms are those that are assessed within 14 days prior to week 1 treatment.

Concomitant medications will be collected from within 14 days prior to enrollment through the study treatment period and maintenance period (see Study Assessments Table section 4.1).

The primary safety endpoint is the occurrence of reported unanticipated problems involving risk to subjects or others (“UPIRTSOs”). These UPIRTSOs are defined as those problems which alter the risks to subjects or others. This includes any study suspensions or holds. The primary safety endpoint analyses will be based on a risk-benefit conclusion.

Effectiveness: There are four instruments measuring participant’s symptoms of chronic pain, anxiety, depression, and sleeplessness. The primary effectiveness endpoint is a statistically significant reduction in one or more of measures of: chronic pain, anxiety, depression, or sleeplessness between baseline and 12 or 24 weeks after initiating treatment.

The null hypothesis to disprove is that there is no statistically significant reduction from baseline to 12 or 24 weeks in mean chronic pain, anxiety,

depression, or sleeplessness symptom severity scores using the Nu-V3 device compared with the usual care cohort.

The instruments used in this study are:

Chronic Pain – Pain intensity (P), interference with enjoyment of life (E), and interference with general activity (G) (PEG Scale),

The PEG is a three-item instrument that measures pain intensity (one item) and pain interference (two items). Each item is valued from 0 (no pain/interference) to 10 (as bad as you can imagine). The instrument score is calculated as the average of the three item values.

Anxiety - Generalized Anxiety Disorder 7-item (GAD-7)

The GAD-7 is a seven-item instrument that measures respondents' symptoms of anxiety. Each item is scored on a four-point Likert scale, and values range from 0 ("Not at all") to 3 ("Nearly every day".) Items are summed to determine the instrument's score. Values of 10 or higher have been associated with moderate anxiety, while values of 15 or higher have been associated with severe anxiety.

Depression - Patient Health Questionnaire (PHQ-9)

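### Optional media testimony is scheduled in the device arm only, between baseline and the week-12 score, which can add an avoidable reporting bias toward the device

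*Protocol*

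**What the plan says.** Section 4.1 of the Protocol has three assessment tables: device arm weeks 1-12, device arm weeks 13-24, and control arm weeks 1-12. Both device-arm tables contain a row headed "Optional Patient Media Testimony". Its footnote (6 in the first table, 5 in the second) reads: "If patient consents to media testimony, site will collect via study collection process". The table headed "Control Arm Evaluation" has neither the row nor the footnote.

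On blinding, section 4.0 states: "The Nu-V3 Clinical Study is a randomized, open-label study". The comparator is observation under standard of care, with no sham device. On the source of the outcomes, section 5.0 states: "The study endpoints data will be collected from each participant's study questionnaires". Section 8.1 places the primary effectiveness endpoint in any of four measures, ending "depression, or sleeplessness between baseline and 12 or 24 weeks after initiating treatment", and frames the null hypothesis as a contrast with controls: "depression, or sleeplessness symptom severity scores using the Nu-V3 device compared with the usual care cohort". The patient-rated global impression of change (PGIC) is a secondary endpoint in section 8.2.

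**The concern.** PEG, GAD-7, PHQ-9 and PROMIS 4a are all completed by patients who know their arm, and so is the PGIC. No primary effectiveness measure is independent of the patient's own report. A patient who has given the site an account of the device for media use, and then completes a symptom questionnaire for the same site, has a reason to answer consistently with that account. Control patients face nothing comparable during the 12 weeks in which the arms are compared. The PGIC is especially close to a testimonial, since it asks for change since treatment began.

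At stake is whether part of a week-12 difference could reflect how patients report rather than how they feel. Analysis could not repair this. Testimony depends on consent and, after baseline, probably on perceived benefit. Adjusting for it, or excluding those who gave it, would condition on a post-randomization variable related to outcome that has no counterpart in the control arm.

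**Working it through.** The Protocol states no figure on this point, so the check is a count from the section 4.1 tables, followed by one illustration on assumed values.

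**Count of marked weeks**

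| Item | Device arm | Control arm |
|---|---|---|
| Testimony, weeks 1-12 | 1, 2, 4, 8, 12 (5) | no row (0) |
| Testimony, weeks 13-24 | 13, 14, 16, 20, 24 (5) | no schedule |
| Patient questionnaires, weeks 1-12 | every week (12) | 1, 4, 8, 12 (4) |
| In-office assessment, weeks 1-12 | every week (12) | 1, 4, 8, 12 (4) |

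Patient questionnaires are due in every device-arm week from 1 to 24, so all 5 + 5 = 10 testimony weeks coincide with outcome collection.

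**Which occasions can affect the week-12 contrast**

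- Week 1 is the baseline visit, when the first device is placed. Testimony then precedes any meaningful experience of treatment.
- Week 12 is the endpoint visit. It matters only if testimony comes before that day's questionnaires, and the Protocol does not give the order.
- Weeks 2, 4 and 8 come after baseline and before the week-12 score, whatever the order on the day.

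The clear exposure is therefore 5 − 2 = 3 occasions in the device arm against 0 in control.

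**Which occasions bear on week 24**

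Weeks 13, 14, 16 and 20 add four occasions before the week-24 score; week 24 itself has the same open question of order. The control table ends at week 12 and section 4.0 then offers controls a crossover to the device. No scheduled control assessment exists at week 24, so these four can affect only change within the device arm.

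**Illustration of sensitivity (assumed values)**

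The Protocol gives no alpha, effect size or standard deviation. Assume two-sided alpha 0.05, a normal two-sample test on one measure, no true effect, and a mean reporting shift of b standard deviations in the device arm only. The chance of a false finding of benefit is Φ(b/√(2/n) − 1.96), with n per arm of 50 to 100 (section 4.0: 100-200 in total, 1:1).

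| b (assumed) | n = 50, √(2/n) = 0.200 | n = 100, √(2/n) = 0.141 |
|---|---|---|
| 0 | 2.5% | 2.5% |
| 0.1 | Φ(0.50 − 1.96) = 7.2% | Φ(0.71 − 1.96) = 10.5% |
| 0.2 | Φ(1.00 − 1.96) = 16.9% | Φ(1.41 − 1.96) = 29.3% |
| 0.3 | Φ(1.50 − 1.96) = 32.3% | Φ(2.12 − 1.96) = 56.4% |

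This shows only that a modest one-sided shift would matter at this sample size, and that enrolling more patients makes it matter more. It is not evidence that testimony produces a shift of any given size.

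**The case against.** The strongest reply is that the tables show very little. The row is optional and depends on consent. A mark denotes an occasion on which testimony may be collected; it does not show that each patient is asked afresh every time, and a single consent at enrolment fits the tables equally well. A reader might infer repeated solicitation, but the document does not support that.

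A reader might also infer that patients have spoken publicly for the product before they rate their symptoms. The Protocol does not say when testimony is released or what it must contain, and the consent pages are not available, so this cannot be asserted either.

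The order on the day is also open. Questionnaires are completed on the patient's own device, and section 4.0 gives part of the visit to verifying that they are complete, so they may well come first. That would remove week 12 from the exposure but leave weeks 2, 4 and 8.

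A third tempting reading is ten occasions against none by week 24. That contrast fails because controls have no schedule beyond week 12.

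Finally, larger asymmetries are already built in: no sham, and twelve in-office visits against four by week 12. Deleting the row would leave them in place, and the separate effect of testimony could not be isolated. This limits the weight of the point but does not answer it. Lack of blinding and unequal contact may be hard to avoid; collecting testimonials during outcome measurement serves no endpoint and is wholly avoidable.

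**Conclusion.** The concern holds in a limited form. Optional testimony about the device is scheduled in one randomized arm only, alongside self-reported outcomes in an open-label trial, and no rule places it after the questionnaires. Three occasions (weeks 2, 4 and 8) clearly precede the week-12 score in the device arm, against none in control. Four more (weeks 13, 14, 16 and 20) precede the week-24 score and bear on within-arm change.

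This can add a reporting bias toward the device. The direction is an inference from inviting testimony in one arm only; the document does not show that scores are in fact shifted, and gives no basis for a size. Any effect would be concentrated in patients who consent. The false-positive rates in the working rest wholly on assumed shifts and do not set the weight of this point. It should be corrected because the remedy is cheap and the analysis cannot provide one.

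**What to change.** Delete the "Optional Patient Media Testimony" row from both device-arm tables in section 4.1, together with footnote 6 (weeks 1-12) and footnote 5 (weeks 13-24). Add a sentence stating that any testimony is collected only after the participant's last endpoint questionnaire: after week 24 for patients randomized to the device, and after the last questionnaire of the crossover period for controls who cross over. A cut-off directly after week 12 would not be enough, because section 8.1 also names week 24 as a primary time point.

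The cost is two table rows, two footnotes and one added sentence. Testimonials arrive later. No endpoint data are lost and no clinical rule changes.
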